6.6 Handling of missing values and outliers

All missing, unused or incorrect data (including midway withdrawal and exit) and unreasonable data will be discussed and finalized by the investigator, sponsor and biostatistician.

Unless otherwise stipulated, missing values of all analysis indicators will not be filled.

7. Monitoring Plan

According to the requirements in *Good Clinical Practice for Medical Devices*, the sponsor shall undertake monitoring responsibilities for the medical device clinical trial, formulate standard operating procedures for monitoring and select monitors who conform to the requirements to fulfill the responsibilities of monitoring:

The monitor number and monitoring frequency shall be commensurate with the complexity of the trial and the number of clinical trial institutions participating in this trial.

The monitors shall be properly trained, be familiar with GCP and relevant laws and regulations, have relevant professional background expertise, be familiar with relevant research materials of investigational medical devices and clinical information of similar products, clinical trial protocol and related documents, and be able to effectively perform monitoring responsibilities.

The monitors shall abide by the standard operating procedures for monitoring formulated by the sponsor, and urge the clinical trial of medical devices to be implemented in accordance with the clinical trial protocol. The aspects to be monitored include the compliance with clinical trial protocol, GCP and relevant laws and regulations by the clinical trial institutions and the

investigators during the conduct of the clinical trial, the signing of informed consent by subjects, screening, follow-up, rights and security protection, management and use of investigational device and control device, management and use of biological samples, handling of adverse events and device defects, reporting of safety-related information, data records of clinical trial and completion of case report forms etc. The monitors shall report to the sponsor in writing after each monitoring which shall include the name of the monitor, monitoring date, monitoring time, site monitored, aspects monitored, name of investigator, project completion information, issues identified, conclusion and the corrective measures taken for the mistakes and omissions etc.

8. Data Management

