6. STATISTICAL ANALYSIS METHODS

6.1 General principles

This study will use SAS 9.4 software or the higher version for statistical analysis.

All statistical tests are conducted using two-sided tests and a P-value less than 0.05 will be considered statistically significant (unless otherwise specified). In this study, hypotheses and statistical inferences are made only for the primary effectiveness indicators, and the intergroup comparisons for the remaining indicators are exploratory analyses.

For the description of quantitative indicators, the number of cases (missing), mean, standard deviation, median, minimum, maximum, and first quartile and third quartile are calculated. The decimal places of the minimum and maximum are kept the same as the original data, but the decimal places of the mean, standard deviation, and median are one more than the original data, but usually, the maximum number of decimal places does not exceed four decimal places.

Qualitative indicators are described by the number of cases and percentages of each category. The percentages are calculated using the non-missing data in each analysis set. Percentages are retained to one decimal place.

All numerically derived variables are retained to two decimal places, unless otherwise specified.

The treatment of missing data will be described in Section 7, otherwise all missing data will be left unfilled.

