6.3 Effectiveness evaluation

6.3.1 Primary effectiveness evaluation

(1) Evaluation Indicators

Overall performance of catheter locking and/or flushing is considered "**pass**" only if: Questions 1 to 4 are answered "Yes" and question 5 is answered "No".

Subjects who do not answer any of questions 1-5 or who answer "not applicable (NA)" will not be entered into the per protocol set; they will be treated in accordance with Table 6.1 when entering the full analysis set.

Table 6.1 Definition of "pass" for different scenarios of primary effectiveness indicators

Questions related to the primary effectiveness indicators	Scenario 1	Scenario 2	Scenario 3	Scenario 4
Whether the effectiveness evaluation is performed?	No	Yes	Yes	Yes
 Whether the air in the pre-filled flush syringe can be removed successfully? Whether the pre-filled flush syringe can be connected to the catheter smoothly? Whether the pre-filled flush syringe can flush and/or lock the catheter successfully? Whether the pre-filled flush syringe can be disconnected from the catheter smoothly? 	NA	Yes	At least one of the answers is "No" for questions 1-4, or "Yes" for question 5	At least one of the answers in Scenario 2 is "NA" or not selected
5. Whether any sites of the flush syringe leak at any time during use?		No		
Primary effectiveness determination (pass/fail)	Missing	Pass	Fail	Missing
Whether to be included in FAS	Yes	Yes	Yes	Yes
Whether to be included in PPS	No	Yes	Yes	No

(2) Evaluation method

The study hypotheses for the primary evaluation indicators are:

Null hypothesis H₀: The overall performance pass rate p_1 in the test device group is inferior to p_2 in the control device group ($p1 \le p2-\delta$);

Alternative hypothesis H₁: The overall performance pass rate p_1 of the test device group is not inferior to p_2 of the control device group $(p_1 > p_2 - \delta)$.

Where $\delta = 5\%$ is the non-inferiority margin, i.e., the range of differences considered not clinically significant.

FAS and PPS are used for evaluation.

Main analysis:

Describe the number and percentage of subjects for whom the two kind of pre-filled flush syringes are used to flush and/or lock the catheter successfully for groups in each study site and all study sites.

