For the primary effectiveness indicator, i.e., overall performance of catheter flushing and/or locking, intergroup comparisons are performed using the Breslow-Day test for parity of effectiveness across sites. The Breslow-Day test is not required if the rate is 100% for both groups in each site, and the effectiveness is considered not statistically different between sites.

A Breslow-Day test with a P > 0.05 means that there is no statistical difference between sites, and the effectiveness data of each site can be combined for analysis. For the difference in the pass rate of the pre-filled flush syringes used to flush and/or lock the catheter in the combined test and control device groups, the 95% confidence interval (CI) for the difference in the pass rate between the two groups is calculated using the Wald method.

A Breslow-Day test with a $P \le 0.05$ indicates a statistical difference between sites, and that the effectiveness data may not be combined for analysis and need to be statistically described separately for each site. Point estimates corrected for site factors are obtained by weighting the difference in the pass rate of the pre-filled flush syringes used to flush and/or lock the catheter by the minimal risk method^[1] for the test device group and the control device group in each site, and the 95% confidence interval (CI) for the difference in the pass rate between the two groups is calculated using the Wald method.

If the pass rate is 100% in both groups, the Newcombe Wilson method ^[2] is used to calculate the 95% confidence interval (CI) for the difference in the pass rate between the two groups.

If the results show that the lower limit of the bilateral 95% confidence interval (CI) for the difference in the pass rate between the test device group and the control device group for pre-filled flush syringes used to flush and/or lock the catheter is greater than -5% (a pre-defined non-inferiority limit), H_0 is rejected and the test device group can be considered non-inferior to the control device group in terms of overall performance pass rate.

The procedure code for calculating confidence interval (CI) about the site-adjusted CMH rate difference is shown below:

/*Variable description: dataset is the input dataset, siteid represents the study site, nurseid represents the nurse, trtp represents the treatment factor, y represents the outcome variable*/

data dataset;

set dataset;

if group="test group" then trt=1;else trt=2;

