/*group is the group variable in the analyzed dataset, and "test group" is generally the value of the group variable, which represents the investigational test device*/

if main="pass" then var=1;else var=2;

/*main is the analyzed variable, and "pass" is generally the dichotomous value of the main variable, which represents the study effect */

run; ods select print; ods output CrossTabFreqs=CrossTabFreqs; proc freq data=dataset; table siteid*trt*var.*Generate a four-cell table; run: quit; proc sort data = dataset; by siteid trt; run; ods select print; ods output BinomialCLs=BinomialCLs; proc freq data=a; by siteid trt; table var/bin(cl=wilson level="1");*Wilson confidence interval is generated in preparation for newcombe method; run; quit; /******Calculate site-adjusted CMH rate difference by using the minimum risk method*** ****************************** proc sql undo policy=none; create table n11 as

select distinct siteid, Frequency as n11

```
from CrossTabFreqs where trt=1 and var=1;
quit;
proc sql undo policy=none;
  create table n12 as
    select distinct siteid, Frequency as n12
    from CrossTabFreqs where trt=1 and var=2;
  ;
quit;
proc sql undo policy=none;
  create table n21 as
     select distinct siteid, Frequency as n21
    from CrossTabFreqs where trt=2 and var=1;
quit;
proc sql undo policy=none;
  create table n22 as
     select distinct siteid, Frequency as n22
    from CrossTabFreqs where trt=2 and var=2;
quit;
data n1234;
  merge n11 n12 n21 n22;*Generate the number of four cells in a four-cell table;
  p1=n11/sum(n11,n12);p2=n21/sum(n21,n22);*Calculate the pass rates of test and control groups: p1,p2;
  p1 p2=p1-p2;
  n=sum(n11,n12,n21,n22);
  diffn=p1 p2*n;
  var=p1*(1-p1)/sum(n11,n12)+p2*(1-p2)/sum(n21,n22); *The variance of the rate difference;
  if var=0 then var 1=1;else var 1=1/var;
 ***If both groups of studies are analyzed at 100%, the variance of the rate difference is 0 and the inverse of
the variance is set to 1:
  dvar 1=p1 p2*var 1;
run;
proc sql undo_policy=none;
  create table riskdiff0 as
    select *,sum(n) as s n,sum(diffn) as s diffn,
        sum(var 1) as s var 1,sum(dvar 1) as s dvar 1
    from n1234;
quit;
data riskdiff;
  set riskdiff0;
  alaph=diffn*s var 1-s dvar 1;
  beta=var 1*(1+alaph*s diffn/s n);
run;
proc sql undo policy=none;
  create table riskdiff as
     select *, sum(alaph*dvar 1) as s advar 1,
        sum(beta*p1_p2) as s_betadif
    from riskdiff;
quit;
data riskdiff;
  set riskdiff:

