7. DATA PROCESSING AND CONVERSION

7.1 Processing of missing data regarding primary effectiveness

The primary effectiveness indicators are not filled.

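### The SAP's printed code counts missing FAS outcomes as failures, while the SAP's written rule leaves them missing

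*SAP*

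**What the plan says.** **Written rule.** In SAP 6.3.1, a subject with any of the five questions unanswered or marked not applicable is left out of the PPS. In the FAS, "they will be treated in accordance with Table 6.1 when entering the full analysis set". Table 6.1 classes two situations as missing: no effectiveness evaluation done (Scenario 1), and at least one item not applicable or not selected (Scenario 4). Both are FAS yes, PPS no. SAP 7.1 adds: "The primary effectiveness indicators are not filled". SAP 6.1 fixes the denominator: "The percentages are calculated using the non-missing data in each analysis set". Protocol 6.6 has the same default, with a qualifier: "Unless otherwise stipulated, missing values of all analysis indicators will not be filled".

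**Printed code.** SAP 6.3.1 introduces its program with "The procedure code for calculating confidence interval (CI) about the site-adjusted CMH rate difference is shown below". The analysed outcome is derived by "if main='pass' then var=1;else var=2". The accompanying comment says the pass label "is generally the dichotomous value of the main variable". The proportions are then formed as "p1=n11/sum(n11,n12);p2=n21/sum(n21,n22"), where n12 and n22 are the counts with var=2 in the test and control arms.

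**Where it applies.** SAP 6.3.1 names both FAS and PPS for the primary evaluation; SAP 5.2 makes the PPS primary. The site-adjusted interval is used when the Breslow-Day P is at or below 0.05. The pooled Wald interval, used otherwise, is described in words with no code.

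**The concern.** The line has two branches for an outcome that Table 6.1 gives three values. A blank or a missing label is not a pass, so it falls through to the failure code. No step in the printed program removes or preserves such records.

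The FAS is the only analysis set that contains missing primary outcomes, so it is the only place where the missing-data rule has any effect, and there the text and the code disagree. A programmer who follows one departs from the other. The choice could then be made after the data are seen, between two FAS results that may fall on opposite sides of the −5% margin.

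**Working it through.** **Inputs.** From the documents: 98% success in both arms, margin 5%, one-sided α 0.025, power 90%, 1:1 allocation, 10% drop-out, 378 subjects (189 per arm), three sites. The documents give no rate of missing outcomes. I assume 2%, 5% and 10%, taking planned drop-out as an upper bound.

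**The plan's sample size reproduces.** n = (1.960 + 1.282)² × 2 × 0.98 × 0.02 / 0.05² = 164.8, so 165 per arm. 165 / 0.9 = 183.3, so 184 per arm and 368 in total. 63 nurses × 6 = 378.

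**One missing outcome, two results.** Under the text it leaves numerator and denominator. Under the code it adds 1 to n12 or n22, and so to the denominator as a failure.

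**Pooled Wald interval** (applies only if the derived variable is reused there). Lower limit = d − 1.96 × √[p1(1−p1)/n1 + p2(1−p2)/n2], 189 randomised per arm, 4 observed failures per arm:

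| Missing (test, control) | Text: test v control | Text: lower limit | Code: test v control | Code: lower limit |
|---|---|---|---|---|
| 8, 8 | 177/181 v 177/181 | −3.03% | 177/189 v 177/189 | −4.92% |
| 9, 9 | 176/180 v 176/180 | −3.05% | 176/189 v 176/189 | −5.10% |
| 4, 0 | 181/185 v 185/189 | −2.98% | 181/189 v 185/189 | −5.64% |
| 0, 4 | 185/189 v 181/185 | −2.89% | 185/189 v 181/189 | −1.41% |

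The last row shows that the recoding is not always conservative: missing outcomes in the control arm help the test device.

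**Site-adjusted interval, worked case.** Three sites of 63 per arm, 3 missing per site per arm, observed failures by site 0, 1, 3 (test) and 3, 1, 0 (control).

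- Text: site differences +5.00, 0, −5.00 points; minimum-risk weights 0.290, 0.420, 0.290; estimate 0; SE 1.515 points; lower limit −2.97%. Breslow-Day P = 0.046, so this branch applies.
- Code: site differences +4.76, 0, −4.76 points; weights 0.322, 0.356, 0.322; estimate 0; SE 2.593 points; lower limit −5.08%.

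Both limits square the weights in the variance, Σw²v. The printed program uses Σwv, a separate matter. With unsquared weights the limits are −5.14% (text) and −8.80% (code), so neither rule shows non-inferiority in this case.

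If the recoded variable also fed the Breslow-Day test, P would be 0.34. The case would move to the pooled branch, where the recoded lower limit is −5.10% (176/189 in each arm).

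**Chance of showing FAS non-inferiority, by simulation.** Missingness is independent of arm and outcome. There were 300,000 trials per rate for the site-adjusted branch (entered on complete-case Breslow-Day P ≤ 0.05, squared weights) and 400,000 per rate for the pooled interval.

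| Missing | Trials on site-adjusted branch | Within that branch, text v code | Overall, line used on that branch only | Pooled interval, if reused, text v code |
|---|---|---|---|---|
| 2% | 3.2% | 88% v 72% | 91.1% to 90.5% | 91% v 72% |
| 5% | 3.0% | 87% v 51% | 91.1% to 90.1% | 91% v 49% |
| 10% | 2.7% | 83% v 34% | 89.4% to 88.1% | 89% v 33% |

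With unsquared weights the within-branch figures are 51% v 24%, 49% v 9% and 44% v 3%.

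**Normal-approximation check of the pooled column.** At 5% missing, the code gives p = 0.98 × 0.95 = 0.931, SE = √(2 × 0.931 × 0.069 / 189) = 0.0261, power Φ(0.05/0.0261 − 1.96) = 48%. The text gives SE = √(2 × 0.98 × 0.02 / 179.55) = 0.0148, power 92%. At 2% and 10% missing the same formula gives 93% v 70% and 91% v 33%.

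**The case against.** The strongest reply is that the block is a template. Its header describes variables the program never uses, one step reads a data set that is not defined, and its comment presumes a two-valued outcome. A pass/fail input is what one would have if Table 6.1, 6.1 and 7.1 had already been applied, and no upstream data preparation is printed. That reading is possible. But the SAP states no such step, and a two-valued outcome contradicts Table 6.1, so the conflict remains on the page.

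Several limits on size stand:

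- The PPS is primary and excludes these subjects.
- The code is labelled for the site-adjusted interval only, a branch reached in about 3% of simulated trials.
- The large losses of power depend on reuse of the variable in the pooled interval, which the SAP does not state.
- The worked reversal on the site-adjusted branch needs squared weights, and needs the Breslow-Day test to be run on complete cases.
- The nurse scores the outcome just after a single flush, so few outcomes may be missing; 10% is an upper bound.
- Protocol 6.6 also refers missing data to discussion by the investigator, sponsor and biostatistician. The denominator rule is in the SAP alone.

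**Conclusion.** The concern holds. As printed, the code turns each Table 6.1 missing outcome in the FAS into a failure, against the SAP's own rule. The PPS result does not change.

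The practical effect ranges from small, if the line acts only on the site-adjusted branch, to large, if its variable also feeds the pooled interval. In the pooled case with 4 observed failures per arm, 9 missing outcomes per arm, or 4 in the test arm alone, are enough to reverse the FAS conclusion. All sizes rest on the assumed missing rates, 98% true success in both arms, three equal sites and, in the simulations, missingness unrelated to arm or outcome.

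The recoding can also turn an observed 100% pass rate into a lower one, and so bypass the SAP's special handling of 100% in both groups. It should be corrected: the conflict is definite, can change a stated FAS conclusion and is cheap to remove.

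**What to change.** Replace the derivation with `if main='pass' then var=1; else if main='fail' then var=2; else var=.;`, so that the code follows Table 6.1. Check that the two labels match the stored values exactly, including case. Otherwise real failures would be set to missing.

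Add one sentence to SAP 6.3.1: the Breslow-Day test, the pooled interval and the site-adjusted interval all use this derivation.

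Optionally, report missing counted as failure as a labelled FAS sensitivity analysis. The complete-case FAS keeps protocol violators that the PPS drops, but it does not test the effect of missing outcomes.

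Cost: one line of code and one sentence, plus one table row if the sensitivity analysis is added. Data collection and sample size do not change.

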3.2 Study population and sample size

The study population includes subjects who require locking and flushing the end of catheter line at the intervals of different drug treatment. Specific inclusion and exclusion criteria are described in the 5.2 Selection of subjects of Protocol.

A total of 378 subjects are proposed to be enrolled in this clinical trial. The study is a parallel-controlled, noninferiority design in which the control device is the BD Pre-filled Flush Syringes, a kind of prevalent product already on the market. The study intends to investigate the overall performance of the test device for flushing and/or locking the catheter that shall be non-inferior to that of the control device. Based on previous clinical experience, the overall performance pass rate of control device for flushing and/or locking the catheter is about 98%, and the study assumes the same treatment completion rate for the test device and control device. This study adopts a non-inferiority design, with α =0.025 (one-sided), β =0.1 (power of 90%), and the non-inferiority margin is 5%. The test group and the control group are allocated 1:1 in equal proportions. The sample size shall be calculated by using the PASS software and 165 subjects shall be enrolled into each of the test group and the control group. However, 368 subjects shall be included in this clinical study considering factors such as dropouts (drop-out rate of 10%) during the trial and other factors.

This study will be performed by 63 authorized nurses who participate in using the investigational device, each nurse will randomly use 3 test devices and 3 control devices, so a total of 378 subjects are proposed to be enrolled in this clinical trial.

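### In the site-adjusted analysis, a site with no failures in either arm gets inverse variance 1, so its weight is near zero and the non-inferiority interval has the wrong width

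*SAP*

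**What the plan says.** SAP 6.3.1 first tests homogeneity across sites. If Breslow-Day P>0.05, the sites are pooled and a Wald interval is used. If P<=0.05, it states: "Point estimates corrected for site factors are obtained by weighting the difference in the pass rate", with minimal risk weights and a Wald interval. Non-inferiority is declared if the lower 95% limit "is greater than -5% (a pre-defined non-inferiority limit").

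The printed SAS program computes each site's variance of the rate difference and inverts it. For a zero variance the rule is "if var=0 then var 1=1;else var 1=1/var" (the gap in the variable name comes from text extraction). The code comment says that this covers sites where both groups are at 100%. It gives no reason for the value 1.

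The Newcombe-Wilson method is reserved for a 100% pass rate in both groups. The text does not describe it for one perfect site among others, and it plans no sensitivity analysis for that case.

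**The concern.** An inverse variance measures information, and 1 is far off the scale of the other sites. At 63 per arm, as failures at a site fall from one per arm to a single failure, the inverse variance rises from 2,017 to 4,033. At no failures it drops to 1. Both terms of the weight formula are multiples of this quantity, so the site with the best results gets almost no weight.

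At stake is the primary decision: in this branch the resulting interval decides whether the null hypothesis is rejected, and a worse test-device result could turn a fail into a pass.

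**Working it through.** **Inputs.** SAP 3.2: a control pass rate where "the overall performance pass rate of control device for flushing and/or locking the catheter is about 98"%, the same rate assumed for the test device, margin 5%, one-sided alpha 0.025, power 90%, and "165 subjects shall be enrolled into each of the test group and the control group". Three sites (SAP 3.1); 378 subjects in total. Protocol 6.1 asks for sites as even as possible, with none above 50% of the total. Assumption: equal sites, 378/3/2 = 63 per arm per site.

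**The plan's own figure.** n per arm = 2 x 0.98 x 0.02 x (1.960+1.282)^2 / 0.05^2 = 164.8, so 165. With 10% dropout, 165/0.9 = 183.3, so 184 per arm and 368 in total; 63 nurses x 6 = 378. This reproduces. The SAP gives no figure for the site weights.

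**Scale of the inverse variance.** For a site with pass rates p1, p2, v = p1(1-p1)/63 + p2(1-p2)/63.

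| Failures at the site | 1/v |
|---|---|
| 98% in both arms (expected) | 1,607 |
| 3 per arm | 695 |
| 1 per arm | 2,017 |
| 1 in one arm only | 4,033 |
| None | 1 (by rule) |

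All failure counts of 0-10 per arm were enumerated at two sites, with the third failure-free. In the 3,710 tables that reach this branch, 1/v at the sites with failures ranges from 236 to 4,033, and the failure-free site's weight from about 0.0002 to 0.0016.

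**Example 1, printed code.** Failures (3,0), (0,3), (0,0). Breslow-Day P = 0.013, or 0.046 if the failure-free site is counted in the degrees of freedom; both trigger the branch. The site differences cancel, so the weights reduce to shares of inverse variance.
- Sites 1 and 2: 1/v = 63/[(3/63)(60/63)] = 1,389. Sum S = 1,389.15 + 1,389.15 + 1 = 2,779.3. Weights 0.4998, 0.4998, 0.0004.
- Printed variance, sum of w x v = 2/2,779.3 = 0.0007196; SE 2.683%. Lower limit 0 - 1.96 x 2.683 = **-5.26%, fail**.
- Only this line changed, with the failure-free site's variance taken from (0.5)/(64) in each arm: 1/v = 4,064, S = 6,842, weight 0.594, variance 3/6,842 = 0.0004385. Lower limit **-4.10%, pass**.
- Printed code, one test-arm failure added at site 3 (Breslow-Day P = 0.028): its 1/v becomes 4,033 and the lower limit is **-4.60%, pass**.
- For contrast, size weights of 1/3 with squared weights: variance (1/9)(2/1,389.15) = 0.000160, lower limit -2.48%. With the added failure, the estimate is -1/189 = -0.53%, the variance (1/9)(2/1,389.15 + 1/4,033) = 0.0001875 and the lower limit -3.21%. The worse result now gives the lower limit, as it should.

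**Example 2, two other code faults corrected.** The alpha term in the weights uses the difference times n where the difference belongs, and the Wald variance sums w x v instead of w^2 x v. With both corrected and this line kept, failures (0,0), (5,0), (0,2) (Breslow-Day P = 0.0075) give inverse variances 1, 862, 2,050 and weights 0.0003, 0.413, 0.587.

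| Handling | Estimate | Lower limit |
|---|---|---|
| This line kept | -1.41% | -5.16% (fail) |
| Size weights | -1.59% | -4.24% (pass) |
| Size weights, failure-free variance 0.5-corrected | -1.59% | -4.43% (pass) |
| Minimal risk weights, 0.5-corrected | -1.41% | -3.95% (pass) |

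**Frequency at a true 98% everywhere.** A site of 126 has no failures with probability 0.98^126 = 7.8%; at least one of three, 1 - (1-0.078)^3 = 22%. Breslow-Day P<=0.05 occurs in 4.4% of simulated trials, and both together in 1.1%. Changing this line alone alters the conclusion in about 0.4% of trials under the printed code, and in about 0.06% once the other two faults are corrected.

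**Direction.** Equal sites: of the 3,710 tables, replacing this line with the 0.5-corrected variance turns 1,380 from fail to pass and none the other way. Sites of 50%/33%/17% with the smallest failure-free: of 3,679 tables, 78 turn from fail to pass and 20 from pass to fail.

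**The case against.** A reader might infer that the failure-free site is in effect deleted and that the adjusted result describes only the other sites. The code does not support that for the estimate, because the site's subjects still enter the total that scales the weights. In Example 2 under the printed code the estimate is -1.59% with this line and -1.59% with the 0.5-corrected variance; actually removing the site gives -2.38%. The damage is to the interval width.

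A reader might also take Example 2 as a reversal under the SAP as printed. It is not: the printed code gives -7.06%, and -6.09% with only this line changed, so it fails both ways. Conversely, Example 1 with the other two faults corrected and this line kept already passes, at -3.72%. Each example depends on how the other faults are handled. That stands, and it is a reason to repair all three together.

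The rule is also prespecified and commented, and the SAP cites references for the minimal risk method and for 100% rates. The documents do not show whether those references support the value 1. Prespecification does not cure a rule under which an extra test-arm failure turns fail into pass.

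Finally, the 0.5 correction is not neutral. It gives the failure-free site a weight of about 0.58-0.59 for a third of the subjects, which narrows the interval. That stands too, and it favours size weights.

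**Conclusion.** The rule is wrong as written and no other provision covers the case. A site with no failures in either arm gets a weight of about 0.02-0.16%. The estimate hardly changes but the interval has the wrong width, usually too wide with equal sites, and the non-inferiority conclusion can reverse. With unequal sites reversals occur in both directions, so it cannot be called uniformly conservative.

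The practical size is small: about 1.1% of trials meet the conditions and about 0.4% change conclusion under the printed code, fewer once the other faults are fixed. These figures assume 98% in every arm and site and 63 per arm per site; the 0.4% takes the 0.5-corrected variance as comparator. The point should be corrected because the repair is cheap and the branch decides the primary result, not because a reversal is likely.

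**What to change.** Correct this together with the alpha term and the squared weights:

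- Remove the zero-variance fallback. Weight sites by size, n1 x n2/(n1+n2), scaled to sum to 1, with variance sum of w^2 x v.
- Preferably give failure-free sites a non-zero variance (0.5-corrected, or through a score or Newcombe interval), so that they do not count as known without error.
- If minimal risk weights are kept, prespecify a non-zero variance for such sites and state the drawback that a 0.5 correction gives the failure-free site a weight of about 0.58-0.59.
- Before database lock, run the program on a test dataset with one failure-free site and confirm that adding a test-arm failure there does not improve the lower limit.

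Cost: an SAP and code edit and one test run, with no additional subjects. Protocol 6.4 does not describe the site-adjusted calculation, so its text need not change.
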